Data will be accessible only to the Study Investigators, study staff, applicable Center staff, UPenn IRB, Office of Clinical Research, authorized UPENN staff (e.g. accounting and billing matters), National Cancer Institute, and the FDA. Communications made among study staff regarding participants will use identification number only and not include names or any other personal identification numbers. Participant data will be kept in locked files which are only accessible to staff. In all data sets we will only include identification numbers to label each participant. No names or other unique identifiers will appear in data sets. Only study-specific staff, identified in institutional review board-approved materials, will have access to the list of names matched to identification numbers. Electronic data will be password protected and will be stored on an institutionally secured and managed server. Per language in our informed consent form and standard procedures across the CIRNA, we retain participant PHI indefinitely unless participants request in writing that they wish to revoke access to this information.

A description of this clinical trial will be available on <http://www.ClinicalTrials.gov>, as required by U.S. Law. This website will not include information that can identify a subject directly. At most, the website will include a summary of the results. Subjects may search this website at any time.

4. Subject Confidentiality:

Information about study subjects will be kept confidential and managed according to the requirements of the Health Insurance Portability and Accountability Act of 1996 (HIPAA). Those regulations require a signed subject authorization informing the subject of the following:

- What protected health information (PHI) will be collected from subjects in this study
- Who will have access to that information and why
- Who will use or disclose that information
- The rights of a research subject to revoke their authorization for use of their PHI.

In the event that a subject revokes authorization to collect or use PHI, the investigator, by regulation, retains the ability to use all information collected prior to the revocation of subject authorization.

How will confidentiality of data be maintained? Check all that apply.

- Paper-based records will be kept in a secure location and only be accessible to personnel involved in the study.
- Computer-based files will only be made available to personnel involved in the study through the use of access privileges and passwords.
- Prior to access to any study-related information, personnel will be required to sign statements agreeing to protect the security and confidentiality of identifiable information.
- Whenever feasible, identifiers will be removed from study-related information.

- A Certificate of Confidentiality will be obtained, because the research could place the subject at risk of criminal or civil liability or cause damage to the subject's financial standing, employability, or liability.
- A waiver of documentation of consent is being requested, because the only link between the subject and the study would be the consent document and the primary risk is a breach of confidentiality. (This is not an option for FDA-regulated research.)
- Precautions are in place to ensure the data is secure by using passwords and encryption, because the research involves web-based surveys.
- Audio and/or video recordings will be transcribed and then destroyed to eliminate audible identification of subjects.
- Other (specify):

Additionally, per NIH policy, sensitive information obtained during the course of the study is protected by under a Certificate of Confidentiality. All recipients of a Certificate shall not:

- Disclose or provide, in any Federal, State, or local civil, criminal, administrative, legislative, or other proceeding, the name of such individual or any such information, document, or biospecimen that contains identifiable, sensitive information about the individual and that was created or compiled for purposes of the research, unless such disclosure or use is made with the consent of the individual to whom the information, document, or biospecimen pertains; or
- Disclose or provide to any other person not connected with the research the name of such an individual or any information, document, or biospecimen that contains identifiable, sensitive information about such an individual and that was created or compiled for purposes of the research.

Disclosure is permitted only when:

- Required by Federal, State, or local laws (e.g., as required by the Federal Food, Drug, and Cosmetic Act, or state laws requiring the reporting of communicable diseases to State and local health departments), excluding instances of disclosure in any Federal, State, or local civil, criminal, administrative, legislative, or other proceeding;
- Necessary for the medical treatment of the individual to whom the information, document, or biospecimen pertains and made with the consent of such individual;
- Made with the consent of the individual to whom the information, document, or biospecimen pertains; or
- Made for the purposes of other scientific research that is in compliance with applicable Federal regulations governing the protection of human subjects in research.

Since self-report data will be collected and stored as part of this study, it is possible that subject privacy or confidentiality can be threatened. To address this concern, the data management system has set up several safeguards to prevent unauthorized access to participant data. In the subject map table, an automatically generated index number is assigned to a subject's study identification number. A linked subject identification table is created to store subject name, address, and telephone contact information. This table uses the automatically generated index number rather than the study identification number. The master subject map and subject identification information are maintained in separate locations. Using this method, no identifying subject information is directly linked to bio-samples or results. Any publication of data will not identify participants by name or with an identifier that could be used to reveal identity.

Video recordings of participants' smoking sessions will not include other identifying information (e.g., name) other than their face. Video recordings will be kept on password-protected computers accessible to study staff only. Recordings will be maintained for a period of at least four years after the study is terminated, completed, or the date that the records are no longer considered necessary.

5. Protected Health Information

The following protected health information (PHI) may be collected as part of this study:

- Name
- Street address, city, county, zip code
- All elements of dates (except year) for dates directly related to an individual and all ages over 89
- Date of birth

- Social Security Number (compensation purposes)
- Telephone number(s) and e-mail addresses
- Results from all questionnaires, tests, and procedures
- Any other unique identifying number, characteristic, or code
- Full face photographic images and any comparable images

Data listed above will be accessible to:

- Investigators and the study team
- Authorized members of UPENN Staff (e.g. accounting and billing matters, provide treatment, etc.)
- UPENN IRB
- Greenphire
- Office of Clinical Research
- The Office of Human Research Protections
- The Food and Drug Administration (FDA)
- The National Institutes of Health

6. Compensation:

Participants will be compensated up to \$100 via ClinCard for successfully completing all study requirements at the end of the single laboratory session (\$90 visit compensation, \$10 travel reimbursement). Those determined to be ineligible during the study session will receive travel compensation only (\$10).

Participants will be asked to complete a W-9 tax form at the conclusion of the study because the University of Pennsylvania is required to report to the Internal Revenue Service (IRS) any cumulative payments for participation in research studies at the University of Pennsylvania that exceed a total of \$600 in a calendar year. A W-9 will aid the Center in tracking and reporting those who participate in multiple projects at the Center and accrue over \$600 in a calendar year.

7. Data and Safety Monitoring:

The PI will be responsible for the overall monitoring of the data and safety of participants, assisted by other study personnel. Any unanticipated problems, serious and unexpected adverse events, deviations or protocol changes will be promptly reported by the PI or designated member of the research team to the IRB.

8. Investigator's Risk/Benefit Assessment:

The PI feels the benefits of study participation outweigh the risks, given that the risks of participating in this study are minimal and largely relate to confidentiality/privacy concerns, and that the anticipated benefits to society include increased knowledge of how cigarette packaging and filtration influence product perceptions, use, and exposure, which by extension, may be used to inform regulation of both cigarette marketing and design to subsequently reduce tobacco-caused disease.

INFORMED CONSENT:

1. Consent Process:

A fully trained study staff member will obtain informed consent using the combined consent and HIPAA authorization form approved by the University of Pennsylvania IRB. The consenting process will occur in-person at the CIRNA prior to the initiation of any study procedures and will involve a discussion of the study requirements and procedures. Participants will have an opportunity to ask any questions and/or express concerns, which will be documented on a "Questions Form." Participants can elect not to participate and may withdraw at any time without penalty. Participants will receive a copy of the combined consent and HIPAA authorization form for their records. In addition, participants will be given the Principal Investigator's contact information (located on the consent) should they wish to speak to the Investigator during the course of the study regarding their consent or the study procedures. The consent process will take place in English. There will be no waiting period, no coercion

to participate, and all participants will be considered competent to provide informed consent (i.e., they will be asked if they understand what they are consenting for). If the participant has difficulty or is unable to understand the consent form or other procedures, they will be excluded from the study. The original signed combined consent/HIPAA authorization and Questions forms will be centrally stored in Regulatory Consent Binders.

2. Waiver of Informed Consent:

Not applicable.

RESOURCES NECESSARY FOR HUMAN RESEARCH PROTECTION:

1. Qualifications of Investigators

Brief highlights are presented below for key investigators.

[name]., Principal Investigator: [name] is an Assistant Professor in the Center for Interdisciplinary Research on Nicotine Addiction (CIRNA) in the Department of Psychiatry and the Tobacco Center of Regulatory Science at the University of Pennsylvania (UPENN). She will oversee operations for the study and will have responsibility for the design, implementation, and evaluation of the proposed research. [name] has previously conducted laboratory-based smoking studies of similar design and duration related to informing the tobacco regulatory science field. She will be responsible for overseeing the study materials for institutional review board approval, programming study equipment, overseeing training, conducting analyses and manuscript preparation.

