Brand appeal: Participants will be asked to complete a 6-item measure of brand appeal regarding their preferred brand and the two study-supplied cigarettes they smoked during their in-person session. They will be asked to rate the design of the brand of cigarette they currently smoke (or just tried) on the following 6 items: 1) stylish, 2) fashionable, 3) cool, 4) high quality, 5) attractive, and 6) appealing. Responses will be scored using a 7-point likert scale with anchors of “Strongly Agree” and “Strongly Disagree.”

Mouth-level nicotine exposure and compensatory smoking: We will collect and store the filters of the two cigarettes smoked during laboratory sessions for potential future analysis regarding mouth-level nicotine exposure (approximated using the biomarker, solanesol) and compensatory smoking (estimated via digital image analysis).

2. Group Modifications:

There will be no differences in study procedures or questionnaire administration; all participants will complete the same procedures and questionnaires following randomization to filter type and packaging conditions.

3. Method for Assigning Subjects to Groups:

Participants will be randomly assigned to smoke two study-supplied cigarettes from 4 possible combinations of filter type and packaging conditions:

1. Charcoal filter cigarette in light-colored pack (NAS Sky cigarette in NAS Sky pack [i.e., actual product])
2. Charcoal filter cigarette in black-colored pack (NAS Sky cigarette in NAS Black pack)
3. Non-charcoal filter cigarette in light-colored pack (NAS Orange cigarette in NAS Sky pack)
4. Non-charcoal filter cigarette in black-colored pack (NAS Orange cigarette in NAS Black pack)

Each participant will smoke one charcoal filtered and one non-charcoal filtered cigarette, in counterbalanced order (i.e., the within-subject condition), but the participant will be assigned the same package color for both cigarettes (i.e., the between subject condition). Randomization group (filter order and package color) will be determined via internal database and assigned prior to participants' arrival for the session.

4. Administration of Surveys and/or Process:

The following measures will be assessed by staff at the start of the laboratory session:

1. Session onset CO
2. Medical history
3. Height and weight
4. Cigarette brand characteristics

The following measures will be completed by participants prior to trying to smoking any laboratory cigarettes:

1. Demographics
2. EtOH

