The Data Manager will develop a module to assist study staff in participant recruitment and retention tracking. This module will accept and store contact information for potential subjects and will include data items to indicate the completion status of significant events. The tracking module will include information about contact and visit schedules to assist in preparing communications to potential and active participants concerning scheduled events. The module will also allow for incentive-related inventory management.

6. Subject Follow-up:

Not applicable. We will not follow up with participants after they complete the single study visit.

STUDY PROCEDURES:

1. Detailed Description:

Telephone eligibility interview (duration: ~0.5 hours): Trained personnel will determine participants' initial eligibility during a structured telephone interview. Those who meet eligibility criteria will be scheduled for the in-person visit.

Laboratory visit (duration: ~2.5 hours): The single study visit will occur at the Center for Interdisciplinary Research on Nicotine Addiction (CIRNA). Upon entering the CIRNA for this session, participants will complete the following:

1. Confirm the accuracy of information (i.e. name, address, phone number, email [if applicable], date of birth, age, ethnicity, race, and cigarette brand type) provided during the initial Telephone Eligibility Screening.
 - a. Participants must bring in a pack of their own preferred brand of cigarettes to verify their cigarette brand type.
 - i. If a participant forgets to bring a pack of their preferred brand of cigarettes, their session may be rescheduled to a later date or the participant may be deemed ineligible at the discretion of the PI.
2. Hear a study description where all study procedures will be reviewed.
 - a. The combined informed consent and HIPAA will be read verbatim. All questions will be answered as appropriate after which the combined informed consent and HIPAA form will be completed (signed and dated) by the participant and a member of the research staff.
3. Perform a CO breath assessment and self-report smoking behavior over the past 24 hours to control for prior tobacco exposure.
 - a. Participants with a CO reading < 5 ppm will be ineligible.
4. Height and weight measurements.
5. Complete a Medical History Form with a member of the research staff to review for applicable contraindications previously listed under Key Inclusion/Exclusion Criteria.

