6. Complete questionnaires on cigarette characteristics (Cigarette Brand Form_*Staff should physically view preferred brand of cigarette pack), demographics, ETOH history, smoking history, nicotine dependence (FTND), craving (QSU), withdrawal (WSC), quitting motivation (contemplation ladder), risk perceptions (Risk Beliefs & Perceived Health Risks), Purchase Task, and Brand Appeal.

7. Smoke two study provided cigarettes interspersed by 45 minutes in the smoking lab while video-recorded.
 - a. Participants will complete a harm perceptions questionnaire before smoking each cigarette.
 - b. CO will be assessed before and after each cigarette smoked in the lab.
 - c. Subjective Cigarette Ratings (VAS), Risk Beliefs, Perceived Health Risks, Purchase Task, Attitudes/Intentions, and Brand Appeal will be assessed after each cigarette smoked in the lab.
 - d. Used cigarette filters will be collected and stored for potential future analysis.
8. Complete the Final Cigarette Rating Scale and NAS & Charcoal Knowledge questionnaires.
9. Receive Debrief Script and study payment
 - a. Participants will be debriefed as to the full purpose of the study and compensated for their time.

2. Data Collection:

As detailed in the Data Management section, we will use both paper and electronic forms (via REDCap) surveys to collect participant data.

3. Genetic Testing:

Not applicable.

4. Use of Deception:

To avoid biasing participants' perceptions and use of the study cigarettes, we will not explicitly state in any materials (e.g., flyers, consent form) that the study's purpose is to evaluate the effects of cigarette packaging and filter composition. Instead, individuals will be told that we are recruiting volunteers to "evaluate different commercially available cigarettes."

Deception is acceptable in the present study because the study is minimal risk, and participants will be debriefed within the same session that the deception occurs.

Deception is necessary and scientifically valid in this instance because we are interested in how certain design and marketing features used to promote cigarettes implicitly affect smokers' perceptions and use of those products; if we were to inform participants that we were specifically interested in their reactions to the filter and packaging, they may respond in ways that they otherwise would not.

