To inform subjects prospectively of the use of deception/incomplete disclosure, we have included the following suggested consent language on our consent document (see Informed Consent document): "In some research studies, the investigators cannot tell you exactly what the study is about before you participate in the study. We will describe the tasks in the study in a general way, but we can't explain the real purpose of the study until after you complete these tasks. When you are done, we will explain why we are doing this study, what we are looking at, and any other information you should know about this study. You will also be able to ask any questions you might have about the study's purpose and the tasks you did. Though we may not be able to explain the real purposes of the study until after you complete the tasks, there are no additional risks to those that have been described in this consent form."

Upon completing the full survey, participants will be debriefed of the true study purpose. They will be told that we were specifically interested in understanding the effects of cigarette packaging and filter type on their perceptions and use of the product, and that we were initially vague about our procedures to avoiding biasing their responses toward the study manipulations.

5. Statistical Analysis:

Analytic plan. Main and interaction effects of filter and pack type will be analyzed using univariate analysis of variance (ANOVA) models in SPSS IBM Statistics v26. Primary outcomes are continuous, and based on previous work^{17,21,22} are expected to meet normality assumptions. Analyses will first include only main and interaction effects, then will include as covariates any baseline variables demonstrating a bivariate association of $p < 0.25$ with a given outcome measure.

Power analysis and sample size. A priori power analyses were conducted for primary aims using G*Power v3.1.9.2. These analyses determined that a target sample size of 40 will be adequate to detect a significant small-to-medium effect (partial $\eta^2 = .05$, $\alpha = 0.05$, within-subject correlation = 0.5) of the 2 x 2 between-within subject interaction on a univariate outcome with 80% power.

RISK/BENEFIT ASSESSMENT:

1. Risks:

The potential risks to participants, and their likelihood and seriousness, are minimal and described below. Participants can choose, as an alternative, to not enroll in this study.

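### The filter and filter-by-pack tests omit cigarette position, so first-versus-second differences stay in the within-person error of Aims 1 and 3

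*Combined protocol and SAP*

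**What the plan says.** Laboratory visit step 3 (Study Procedures, 1. Detailed Description) has staff "Perform a CO breath assessment and self-report smoking behavior over the past 24 hours to control for prior tobacco exposure". This gives one set of values per person, taken before either study cigarette. At step 7 participants "Smoke two study provided cigarettes interspersed by 45 minutes in the smoking lab while video-recorded".

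Under Methods, 3. Method for Assigning Subjects to Groups, "Each participant will smoke one charcoal filtered and one non-charcoal filtered cigarette, in counterbalanced order", with the same pack for both. Order is part of the allocation: "Randomization group (filter order and package color) will be determined via internal database and assigned prior to participants' arrival for the session".

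Study Procedures, 5. Statistical Analysis states: "Main and interaction effects of filter and pack type will be analyzed using univariate analysis of variance (ANOVA) models in SPSS IBM Statistics v26". It continues: "Analyses will first include only main and interaction effects", and "then will include as covariates any baseline variables demonstrating a bivariate association of $p < 0.25$ with a given outcome measure". It does not mention cigarette position or filter order, a subject term, the SPSS procedure, or the form in which covariates enter. The sample size rests on the between-within interaction: partial eta-squared 0.05, alpha 0.05, within-subject correlation 0.5, N = 40 and 80% power.

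**The concern.** The two cigarettes are not smoked under the same conditions. The first follows the participant's own smoking by an interval that the protocol does not fix. The second follows a study cigarette by 45 minutes. Puffing, ratings and CO boost may differ between first and second for that reason alone.

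Counterbalancing gives such a shift opposite signs in the two order groups, so it averages out of the filter and interaction estimates. It does not leave their error variance unless position or order is in the model. The design randomises order, and the analysis does not use it. At 80.7% power the interaction that sized the trial has almost nothing to spare.

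The prior-smoking measures raise a related question. If prior exposure acts mainly on the first cigarette, its effect on charcoal minus non-charcoal also changes sign with order. A covariate crossed with filter would then miss it.

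**Working it through.** **1. The plan's own figure.** Inputs from the power statement: partial eta-squared 0.05, correlation 0.5, N = 40, two measurements, two groups.
- f² = 0.05/0.95 = 0.0526, so f = 0.229.
- λ = f² × N × 2/(1 − 0.5) = 0.0526 × 40 × 4 = 8.42.
- Power from the noncentral F with 1 and 38 df is 80.7%. The smallest even N that reaches 80% is 40. The figure reproduces.

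**2. The same test on differences.** Let D be a person's charcoal value minus the non-charcoal value, in SD units. Var(D) = 2(1 − 0.5) = 1. The interaction is the pack difference in mean D, which is 4f = 0.918. Check: 0.918²/[1 × (1/20 + 1/20)] = 8.42.

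**3. Additive prior smoking.** If prior smoking X adds bX to both cigarettes, bX drops out of D. In simulation without a covariate, raising b from 0 to 2 SD left interaction power at 80.8% and 80.7%. A 1 SD pack imbalance in X gave a bias of 0.001. Nothing is left here to control.

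**4. Position shift.** Let the first-minus-second shift be δ, the same for both filters. D then contains +δ when charcoal is first and −δ when it is second. With 10 people per order-by-pack cell the means are unaffected. With order left out, the residual variance of D becomes 1 + δ².

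| Assumed δ | Residual variance | λ = 8.42/(1 + δ²) | Power, noncentral F | Power, simulated | Power with position term |
|---|---|---|---|---|---|
| 0 | 1.00 | 8.42 | 80.7% | about 81% | about 81% |
| 0.3 | 1.09 | 7.73 | 77.3% | about 78% | about 81% |
| 0.5 | 1.25 | 6.74 | 71.6% | about 73% | about 81% |

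The noncentral F is slightly low because the shift adds a fixed amount, not a random one, to the residual sum of squares. With the position term the error df falls from 38 to 37, and power is 80.7% at every δ.

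**5. Optional exposure-by-position term.** Suppose X explains a share x of first-cigarette variance, with the total Var(D) held at 1, and let the second-cigarette slope be r times the first. The share of Var(D) due to X is x(1 − r)². Simulated interaction power at N = 40, for x = 10% to 30%:

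| Second slope relative to first | Share removable | Power with exposure × position |
|---|---|---|
| none (r = 0) | 10%, 20%, 30% | about 84%, 87%, 91% |
| half (r = 0.5) | 2.5%, 5%, 7.5% | about 81 to 82% |
| equal (r = 1) | 0 | about 1 point below no covariate |

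In the first row, covariate × filter leaves power at about 80%, because the effect on D has opposite signs in the two order groups.

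**The case against.** The strongest reply is that nothing is in error. Order is counterbalanced and pack is randomised, each person is their own control, the promised power reproduces, and the study is a pilot. All of that stands. It limits the point to precision.

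A reader might infer that, because a person-level covariate cancels from a within-person difference, Aims 1 and 3 are left uncontrolled for prior smoking. The documents do not support this. The covariate cancels because an equal effect on both cigarettes cancels with it. The Analytic plan never says that covariates enter additively. Step 3 names no aim: the measure can serve the between-person pack test (Aim 2), and the CO reading is also an eligibility check.

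Three further replies have force.
- CO is read before each cigarette, so exposure-by-position is not the only way to represent position-specific exposure, and CO boost already uses that reading. The reading before the second cigarette is, however, taken after the first study cigarette and may carry its effect, so it is not a baseline covariate.
- The protocol describes onset CO as reflecting daily exposure, which may act similarly on both cigarettes. Consent, measurements and questionnaires also come before the first cigarette and partly limit variation in recent smoking. Both lower the gain to expect from the optional term.
- The source of the 0.5 correlation is not given. If it already absorbs a position shift, the stated 80% holds without the term, and adding position would raise power above it.

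**Conclusion.** The point holds as a modest loss of precision. The planned filter and interaction tests leave first-versus-second differences in their error term, although order is randomised and known. With a shift of 0.3 to 0.5 SD, interaction power at N = 40 is about 78% to 73% without a position term and about 80% with it.

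This assumes a within-person analysis (the one the power statement describes), a correlation of 0.5 net of position, equal order-by-pack cells, and a shift common to both filters. The documents give no value for the shift. If it is zero, the term costs almost nothing.

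A reader might also take 84% to 91% as power that the plan gives away by not modelling prior smoking. That range needs prior smoking to explain 10% to 30% of first-cigarette variance and none of the second. No section supports those values, and the gain shrinks or reverses as the two slopes converge. Only the position term is a clear improvement.

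**What to change.** In Statistical Analysis, state that the filter and filter-by-pack tests use a within-person model that includes cigarette position (first or second). Equivalently, regress the charcoal-minus-non-charcoal difference on pack and filter-order group. Include the term in every such model, without the p < 0.25 screen. The cost is one sentence and one degree of freedom, with no extra participants or data.

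As a declared precision option, pre-specify one centred baseline-exposure × position term, using session-onset CO or the 24-hour self-report already collected at step 3, also outside the screen. It costs one further degree of freedom. State that it helps only if prior smoking acts more on the first cigarette than on the second, and that about 1 point of power is lost if it acts equally. A covariate × filter term is not a substitute.
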